### RESPID is response ID, a sequential numbering of the dataset observations
### SUBJIDN is an integer valued SUBJID, a sequential numbering of unique subjects
for(i in 1:length(survey$RESPID)) {
 for(j in 1:max(SUBJIDN)) {
  if(survey$SUBJID[i]==startday$SUBJID[j]) {
   survey$DAY[i] <- as.numeric(survey$DATE[i]) - as.numeric(startday$DATE[j])</pre>
   survey$WEEK[i] <- (as.numeric(survey$DAY[i]) %/% 7)+1
   survey$METH01[i] <- as.integer(survey$METH[i]=='Methamphetamine')
   if(is.na(survey$METH01[i])) {survey$METH01[i]=0}
setDT(survey)
weeksdat <- survey[,list(usedays=sum(METH01)), by=.(TRT GRP,SUBJID,WEEK)]
# Add some jittering to be able to distinguish and follow individual participants
for(i in 1:length(weeksdat$usedays)) {
 weeksdat\usedays i[i] = weeksdat\usedays[i]+rnorm(1,mean=0,sd=.05)
# Spaghetti plot
plot <-ggplot(data=weeksdat, aes(x=WEEK, y=usedays j, group=SUBJID))
plot +
 geom line(aes(col = TRT GRP)) +
 #geom point() +#
 xlim(0,25) +
 v_{1}(-.25,7.25) +
 labs(title = "Spaghetti Plot of Participant Weekly Meth Use Days\n",
    x="Study Week", y="Number of Meth Use Days", color="Treatment Group\n") +
 scale x continuous(breaks=seq(0,26,2)) +
 scale y continuous(breaks=seq(0,7,1))
 theme bw()
```

Exhibit 8 Weekly Meth Use Days Spaghetti Plot

Spaghetti Plot of Participant Weekly Meth Use Days

Proportion of participants with *n* or fewer use days between Week 5 and Week 25 Measured by Self-Report

The proportion of participants with n or fewer use days between Week 5 and Week 25, where n ranges from 0 to 20 will be summarized. A secondary endpoint is Complete Abstinence during the last 4 weeks. This analysis will expand that to the last 20 weeks and explore a range of use days from 0 (complete abstinence) to 20 (an average of one use day a week).

A "use day" or "abstinent day" will be based on self-report surveys. Missing survey responses will be imputed assuming use for that day. The summary will be descriptive only, presenting the number and percentage of "responders," defined as subjects with n or fewer use days between Week 5 and Week 25 (Study days 29 to 169). A continuous responder curve will be produced with the number of use days on the horizontal axis and percent of subjects on the vertical axis, with a line for each treatment group. Since the criteria for a responder becomes less strict as n increases, both curves would be expected to be near 0% at n=0, and increase as they move to the right. The graph will allow a visual examination of potential separation between treatment groups. Pseudo-R code for the plot is included in Exhibit 9. For number of use-days from 0 to 140 (20 weeks), calculate the proportion of subjects with n use-days or less. Exhibit 10 shows an example of the plot.

Exhibit 9 Pseudo-R Code for Continuous Responder Curve Plot

[figure not shown]
plot(NA,NA,xlim=c(0,175),ylim=c(0,1),xaxt='n',yaxt='n',xlab='Number of Use Days', ylab='Proportion of Responders',main='Continuous Response Curve') for(i in 1:18){

```
abline(v=(i-1)*10,col=rgb(0,0,0,0.05))
}
for(i in 1:11){
   abline(h=(i-1)/10,col=rgb(0,0,0,0.05))
}
lines(seq(0,max(trt$DAY)),prop_resp_t,col=rgb(0.2,0.7,0.9,1))
lines(seq(0,max(placebo$DAY)),prop_resp_c,col=rgb(1,0.5,0,1))
   axis(1,seq(0,180,10))
   axis(2,seq(0,1,0.1))

legend(125, 0.2, legend=c('Treatment','Placebo'),
   col = c(rgb(0.2,0.7,0.9,1),rgb(1,0.5,0,1)),lwd=c(1,1))
```

Exhibit 10 Continuous Responder Curve Plot

Continuous Responder Curve

Proportion of participants with *n* or fewer use days between Week 5 and Week 25 Measured by Saliva Screens

The proportion of participants with n or fewer use days between Week 5 and Week 25, where n ranges from 0 to 20 will be summarized. A secondary endpoint is Complete Abstinence during the last 4 weeks. This analysis will expand that to the last 20 weeks and explore a range of use days from 0 (complete abstinence) to 20 (an average of one use day a week).

A "use day" or "abstinent day" will be derived using the following algorithm.

- If a participant has two positive tests, misses two tests, or has one positive and one missing test in a given week, then impute 7 use days for that week.
- If a participant has one positive/missing test and one negative test, then impute 4 use days for that week.
- If a participant tests negative for both tests, then impute 0 use days for that week.

The summary will be descriptive only, presenting the number and percentage of "responders," defined as subjects with n or fewer use days between Week 5 and Week 25. A continuous responder curve will be produced with the number of use days on the horizontal axis and percent of subjects on the vertical axis, with a line for each treatment group. Since the criteria for a responder becomes less strict as n increases, both curves would be expected to be near 0% at n=0, and increase as they move to the right. The graph will allow a visual examination of potential separation between treatment groups.

4.9. Pharmacokinetics Endpoints

The PK Concentration Set will be used for serum concentration summaries and listings and the PK Parameter Set will be used for PK parameter summaries and listings as specified in this section.

PK analyses will be conducted for IXT-m200 by treatment group as described below. The non compartmental analysis (NCA) will be performed using appropriate software, i.e., PhoenixTM WinNonlin® (Version 8.3 or higher, Certara Corporation). All other analyses will be performed using SAS® (Version 9.4 or higher, SAS Institute Inc).

4.9.1. PK Sampling Schedule

Section 1.3.2 of the protocol contains the full participant schedule for the PK subset.

- In all main study subjects, blood samples will be taken for analysis of IXT-m200 in serum on Day 1, Day 29, Day 57, Day 85, Day 113, and Day 141 at pre-dose (≤30 min prior) and 4 hours (±10 min) after the start of dosing, and once each visit on Day 169, Day 197, Day 225, and at early termination.
- In subjects in the PK subset, blood samples will be taken for analysis of IXT-m200 in serum on Day 1 and Day 141 at pre-dose (≤30 min prior), 1 hour (±10 min) and 4 hours (±10 min) after the start of dosing, and once at each visit on Day 2, Day 8, Day 15, Day 22, Day 142, Day 148, Day 155, and Day 162. Blood samples will also be taken at pre-dose and 4 hours after the start of dosing on Day 29, Day 57, Day 85, and Day 113, and once each visit on Day 169, Day 197, Day 225, and at early termination.

4.9.2. Handling of the Difference between the Scheduled and the Actual Sampling Times

For all sampling times, the actual sampling times will be calculated as the difference between the sample collection actual clock time and the actual clock time of start of dosing. The actual post-

dose sampling times expressed in hours and rounded off to three decimal digits will be used to calculate the PK parameters, except for pre-dose samples occurring prior to dosing (pre-dose), which will always be treated as zero (0.000), regardless of the time difference. Scheduled sampling times will be presented in concentration tables by treatment group.

4.9.3. PK Endpoint

Available serum IXT-m200 data up to 28 days after dosing on Day 1 and Day 141 from the PK Parameter Set will be used to calculate the PK parameters.

The following PK parameters will be calculated for Day 1, if the data are sufficient to generate a reliable parameter estimate:

 AUC_{0-t} : Area under the concentration-time curve from time zero to the last non-zero

concentration, calculated using the linear up, log down trapezoidal method.

AUC_{0-28d}: Area under the concentration-time curve from time zero to day 28, calculated

using the linear up, log down trapezoidal method.

AUC_{0-inf}: Area under the concentration-time curve from time zero to infinity

(extrapolated), calculated as $AUC_{0-t}+C_t/K_{el}$, where: C_t = the last observed

non-zero concentration.

C_{max}: Maximum observed concentration.

Residual area: Residual area, calculated as 100*(1- AUC_{0-t} / AUC_{0-inf}). If Residual area is

>20%, any PK parameters derived from AUC_{0-inf} will be flagged in individual

listings.

 T_{max} : Time of observed C_{max} .

 $t_{i,j}$: Elimination half-life, calculated as $log(2)/K_{el}$ using the natural logarithm.

K_{el}: Elimination rate constant. This parameter will be the negative of the

estimated slope of the linear regression of the ln-transformed serum

concentration versus time profile in the terminal elimination phase. The Best-fit method, in Phoenix WinNonlin, will be used to calculate the K_{el} from at least 3 concentration data points excluding the C_{max} . Rsq adjusted, the goodness of fit statistic for the terminal elimination phase, adjusted for the number of points used in the estimation of K_{el} must be ≥ 0.8 . The timepoint where ln-linear K_{el} calculation begins (K_{el} Lower) and the actual sampling time of the last measurable concentration used to estimate the K_{el} (K_{el} Upper), as well as the Rsq adjusted for the ln-linear regression for the calculation of the elimination rate constant will be reported. If the K_{el} cannot be measured (e.g.: fewer than 3 non-zero concentrations in the terminal elimination phase or Rsq adjusted <0.8), then elimination related PK parameters (K_{el} , K_{el} Lower, K_{el} Upper, AUC_{0-inf}, Rsq adjusted, Residual area, $t_{1/2}$, CL and V) will be presented in the listing with a flag and excluded from descriptive statistics.

CL: Clearance, calculated as Dose/AUC_{0-inf}.

V: Volume of distribution, calculated as Dose/(K_{el} x AUC_{0-inf}).

The following PK parameters will be calculated for Day 141, if the data are sufficient to generate a reliable parameter estimate:

AUC_{0-t}: Area under the concentration-time curve from time zero to the last non-zero

concentration, calculated using the linear up, log down trapezoidal method.

AUC_{0-tau}: Area under the concentration-time curve over the dosing interval (tau = 28

days) at steady-state.

C_{max,ss}: Maximum observed concentration at steady-state.

 $T_{\text{max,ss}}$: Time of observed C_{max} at steady-state.

 $t_{1/2}$: Elimination half-life, calculated as $log(2)/K_{el}$ using the natural logarithm.

K_{el}: Elimination rate constant. This parameter will be the negative of the

estimated slope of the linear regression of the ln-transformed serum concentration versus time profile in the terminal elimination phase. The Best-fit method, in Phoenix WinNonlin, will be used to calculate the $K_{\rm el}$ from at least 3 concentration data points excluding the $C_{\rm max}$. Rsq adjusted, the

goodness of fit statistic for the terminal elimination phase, adjusted for the number of points used in the estimation of K_{el} must be ≥ 0.8 . The timepoint where ln-linear K_{el} calculation begins ($K_{el \ Lower}$) and the actual sampling time of the last measurable concentration used to estimate the K_{el} ($K_{el \ Upper}$), as well as the Rsq adjusted for the ln-linear regression for the calculation of the elimination rate constant will be reported. If the K_{el} cannot be measured (e.g.: fewer than 3 non-zero concentrations in the terminal elimination phase or Rsq

adjusted <0.8), then elimination related PK parameters (K_{el}, K_{el Lower}, K_{el Upper},

Rsq adjusted, t_{1/2}, and V_{ss}) will be presented in the listing with a flag and

excluded from descriptive statistics.

CL_{ss}: Clearance at steady-state, calculated as Dose/AUC_{0-tau}.

V_{ss}: Volume of distribution at steady-state, calculated as Dose/(K_{el} x AUC_{0-tau}).

RC_{max}: Accumulation ratio based on C_{max}, calculated as C_{max} on Day 141/Day 1

RAUC: Accumulation ratio based on AUC, calculated as AUC_{0-tau} Day 141/AUC_{0-28d}

Day 1

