1.3.2 PK SUBSET PARTICIPANT SCHEDULE

Assessment ^a	Screening	Dosing (-2/+7 days)										Follow-up (±3 days)			ET			
		≤-1	1				5	9	13	17	21			25	29	33	NA	
Study Week	≤-1	1 ^b					29	57	85	113	141				169	197	225	NA
Study Day	-15 to -1	1 ^b													169	197	225	NA
PK Sample Collection Day			2 (+1)	8 (±2)	15 (±3)	22 (±3)							142 (+1)	148 (±2)	155 (±3)	162 (±3)		
Informed consent	X																	
Initial evaluations ^p																		
Eligibility criteria																		
Demographics																		
Medical history and medications																		
Vital signs ^c																		
Physical exam																		
Psychiatric exam (e.g., C-SSRS)																		
Urine pregnancy test																		
Saliva drug screen																		
Drug use assessment via DSM-5 ^m																		
Laboratory tests ^d	X	X					X	X	X	X	X				X		X	
Electrocardiogram (ECG) ^e	X	X					X	X	X	X	X							
App training																		
App download and tutorial ^q																		
Saliva drug screens (up to 4) ^k	X																	
Recovery coaching ^j																		
Adverse Outcomes Assessment	X							X							X		X	X
Quality of Life Assessments - TEA ^f																		
Quality of Life – PGIC and CGIC ^f								X							X		X	X
METH Use Assessments ⁿ	X														X		X	X
Randomization		X																
Blood for PK ^g	X	X	X	X	X	X	X	X	X	X	X	X	X	X	X	X	X	X
Blood for HACA ^o	X						X		X						X		X	X
Blood for Cytokines ^l	X					X	X	X	X	X								
Dose administration ^h	X					X	X	X	X	X								
Cognitive behavioral therapy	X					X	X	X	X	X						X		
Wellness check																		
Update medical history																		
Update medications																		
Brief psychiatric evaluation																		
Vital signs ^c																		
Targeted physical exam															X		X	X
Urine pregnancy test																		

Assessment ^a	Screening	Dosing (-2/+7 days)										Follow-up (±3 days)			ET			
		≤1	1				5	9	13	17	21			25	29	33	NA	
Study Week	≤1	1					5	9	13	17	21			25	29	33	NA	
Study Day	-15 to -1	1 ^b					29	57	85	113	141				169	197	225	NA
Continuous events AE monitoring ⁱ Recovery coaching ^j Self-report daily drug use by app Random saliva drug screens ^k		Continuous																

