4.9.4.2. Listing and Presentation of Individual PK Data

- The sampling time of pre-dose samples relative to dosing is treated as zero for all sampling periods separately
- All concentrations are presented in original units as reported by the Bioanalytical laboratory
- All concentrations that are below the limit of quantification (BLQ) are set to zero
- Listings of PK sampling times include nominal and actual time elapsed from dose with the deviation from the nominal time and measured concentrations of the drug
- No further imputation will be applied to any missing values

Individual IXT-m200 concentration data will be listed by subject, visit, timepoint, and treatment group.

An overlay plot (Spaghetti plot) of subjects by treatment group will be presented graphically on both linear and semi-logarithmic scales for IXT-m200.

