4.9.5. PK Parameters Derivation

For the derivation of PK parameters, the following rules will apply:

- All concentration values below the assay's lower limit of quantification (BLQ) will be treated as zero
- The sampling time of pre-dose samples relative to dosing will also be treated as zero
- Actual blood sampling times will be used to derive PK parameters (if the actual blood sampling is not present, then that timepoint and concentration will not be considered for PK analyses (except for predose, where timepoint as zero will be considered))
- No further imputation will be applied to any missing values

Individual IXT-m200 PK parameters will be listed by subject, visit, and treatment group.

Additionally, box plots of PK exposure parameters (e.g., AUC, C_{max}) and HACA results may be presented, as appropriate.

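### SAP 4.9.3 cuts the Day 1 PK profile at 28 days although dose 2 may fall at 26–35 days, so a late visit loses the sample that closes the first interval and an early one can let in a post-dose-2 sample

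*SAP*

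**What the plan says.** - **Data cut-off.** SAP 4.9.3 takes "Available serum IXT-m200 data up to 28 days after dosing on Day 1 and Day 141 from the PK Parameter Set" for the parameters of both profiles.
- **Which clock.** SAP 4.9.5 states: "Actual blood sampling times will be used to derive PK parameters". SAP 4.9.2 likewise uses actual times for parameters and keeps scheduled times for the concentration tables.
- **Time zero.** SAP 4.9.2 makes an exception for "pre-dose samples occurring prior to dosing (pre-dose), which will always be treated as zero (0.000), regardless of the time difference". SAP 4.9.5 repeats it: "The sampling time of pre-dose samples relative to dosing will also be treated as zero". SAP 4.9.4.2 gives the scope: "The sampling time of pre-dose samples relative to dosing is treated as zero for all sampling periods separately". None of the three says how a pre-dose sample is handled when it also closes the previous interval.
- **Samples.** In the PK subset (SAP 4.9.1) the first interval has samples on Day 1 (pre-dose, 1 h, 4 h) and on Days 2, 8, 15 and 22. The next is the Day 29 pre-dose sample, nominally 28 days after dose 1.
- **Visit window.** Protocol 1.3.2 gives dosing visits the window headed "Dosing (-2/+7 days". Day 22 has ±3 days.
- **Use of the result.** In SAP 4.9.3, AUC0-28d after dose 1 is the denominator of RAUC. No rule is given for reaching day 28 when no sample lies there. AUC0-28d is also not among the parameters flagged and left out of the summaries when Kel cannot be measured.

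**The concern.** The cut-off is a fixed 28 days, while the sample that should close the interval moves with the dose 2 visit. At a late visit that sample still reflects dose 1 alone, because no second dose has been given. It is valid terminal-phase information, yet it falls outside the limit. At an early visit the limit runs past dose 2, and nothing in 4.9.3 keeps the 4-hour post-dose-2 sample out of the Day 1 profile.

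The time-zero rule adds a second ambiguity. Taken literally, the pre-dose-2 sample has only one time, zero, and could be left out of the Day 1 profile for everyone.

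At stake are the Day 1 Kel, half-life, AUC0-inf, CL and V, and the denominator of RAUC. Which data enter would depend on how punctual the dose 2 visit was. The closing sample of the Day 141 profile (Day 169) is not pre-dose, so the time-zero rule does not touch it. Numerator and denominator of RAUC may therefore be closed differently.

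**Working it through.** The documents give no figure for AUC0-28d, its extrapolated share or RAUC, so there is no plan figure to reproduce.

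**Inputs.** Protocol 2.2 gives a half-life of about 18 days, a volume of about 5 L and a clearance of about 200 mL/day. These agree with each other: ln2 × 5 / 0.2 = 17.3 days. Mono-exponential decline is assumed, with k = ln2/18 = 0.0385 per day.

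**1. Timing.** Dose 2 at Day 29 −2/+7 falls 26 to 35 days after dose 1, which is 10 calendar days. Days +1 to +7 put the sample past 28 days: 7 of 10. On the nominal day, inclusion turns on the clock time. With dose 2 at 26 or 27 days, the 4-hour sample is at about 26.2 or 27.2 days, inside the limit.

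**2. Area beyond the last sample** if the profile ends at 21 days:
- share = (e^(−21k) − e^(−28k)) / (1 − e^(−28k)) = (0.445 − 0.340) / (1 − 0.340) = 0.160
- 13.8% to 18.3% for assumed half-lives of 14 to 25 days
- 24.2% or 8.6% if Day 22 is sampled 3 days early or late

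**3. Effect on AUC0-28d and RAUC.**
- *Extrapolated with Kel:* a Kel 30% too low or too high shifts AUC0-28d by +0.6% or −0.6%. In a simulation with an assumed bi-exponential profile, the SD of AUC0-28d rose from 4.7% to 4.9% at 10% noise and from 9.5% to 10.0% at 20% noise, with no added bias.
- *Truncated at 21 days:* true RAUC at dose 6 = (1 − e^(−168k)) / (1 − e^(−28k)) = 0.998 / 0.660 = 1.51. Truncation multiplies it by 1 / (1 − 0.160) = 1.19, giving 1.80.

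**4. Precision of Kel.** For fixed points, the slope standard error is proportional to 1/√Sxx.
- 7, 14, 21 days: Sxx = 98. Adding 28 days: Sxx = 245. Ratio √(245/98) = 1.58.
- With Day 2 (1 day post-dose) as well: Sxx = 224.75 and 462.8. Ratio √(462.8/224.75) = 1.43.

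**5. The adjusted Rsq rule.** SAP 4.9.3 needs at least 3 points and adjusted Rsq ≥ 0.8. Simulated with mono-exponential decline, an 18-day half-life, independent log-scale noise, and the best adjusted Rsq among fits to the last 3 or more points:

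| Noise (assumed) | Points eligible | Fail with closing sample | Fail without |
|---|---|---|---|
| 10% | from Day 8 | about 6% | about 22–23% |
| 10% | from Day 2 | about 1% | about 7% |
| 20% | from Day 8 | about 40% | about 55% |
| 20% | from Day 2 | about 28% | about 41% |

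Protocol 4.1 plans about 12 active PK participants per cohort, and SAP 1.2 says Cohort 2 was not enrolled. If all 12 lost the sample, the extra failures at 10% noise would be about 12 × (0.22 − 0.06) = 1.9 profiles, or 12 × (0.07 − 0.01) = 0.7 if Day 2 is eligible.

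**6. Residual area.** This is 34.0% from 28 days and 44.5% from 21 days. Both exceed the SAP's 20% flag, so the flag does not separate the two cases.

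**The case against.** The strongest reply is that the SAP, read as a whole, means to use the sample. SAP 4.9.4.2 sets time zero relative to dosing and separately for each period, so the same sample can be time zero for dose 2 and a post-dose sample for dose 1. A Day 29 pre-dose draw, an AUC to day 28 and a limit of 28 days fit together naturally. This stands for early and on-time samples: the 28-day limit itself admits them. A reader might infer that the SAP discards the sample for every participant and extrapolates AUC0-28d from Day 22. The documents support neither part. No section excludes the sample by name, and none says how day 28 is reached.

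SAP 4.9.3 also does not say in terms that its 28 days are actual rather than nominal. But 4.9.2 and 4.9.5 prescribe actual times for parameters, so a late sample falls outside the limit as written.

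On size, it is fair to say that 16% is area, not error, and that a usable Kel recovers it almost fully. The slope ratios hold for fixed points, whereas the SAP lets the software choose them. PK staff also judge whether each profile is adequate (SAP section 3), and would probably not mix a post-dose-2 sample into the Day 1 profile. RAUC is only summarised descriptively. These points limit the consequence. They do not supply the missing rule.

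**Conclusion.** The point holds for late visits on the SAP's stated rules, and for early visits because no rule limits Day 1 data to samples before dose 2. For on-time samples there is only an ambiguity in the time-zero wording.

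The main cost is to Kel and what depends on it: a slope standard error 1.4–1.6 times larger and more profiles failing the adjusted Rsq rule. AUC0-28d is hardly affected if the tail is extrapolated with a reliable Kel. The RAUC shift from 1.51 to 1.80 arises only if the area stops at the last sample, which the SAP neither states nor rules out.

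The 7-in-10 figure counts allowed days. It should not be read as the share of participants who would lose the sample, since the documents give no distribution of visit dates. The sizes rest on mono-exponential decline, an 18-day half-life and assumed noise of 10% or 20%. This is a secondary, descriptive analysis, but it rests on about 12 active profiles, each about 8% of the data (1/12), and the correction is nearly free.

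**What to change.** Amend SAP 4.9.2, 4.9.3 and 4.9.5 before the PK parameters are derived:

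1. The sample taken before dose 2 enters the Day 1 profile at its actual elapsed time from the start of the dose 1 infusion, whatever that time is. It keeps time zero only in the dose 2 profile.
2. The Day 1 profile uses only samples drawn before dose 2. This replaces the 28-day limit for that profile.
3. AUC to exactly 28 days is obtained by log-linear interpolation when the last sample is later than 28 days, and by extrapolation with Kel when it is earlier.
4. The same 28-day rule applies to the Day 169 sample for AUC0-tau. Its ±3-day window puts it at 25 to 31 days if dose 6 is given on its nominal day.
5. AUC0-28d and RAUC are flagged when they rest on a Kel that fails the SAP's criteria.

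The sample and the clock times are already planned for collection, and visit windows need not change. The cost is SAP wording and one derived time variable.
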